6.1.2 Adverse Event Severity

The investigator will rate the severity of each adverse event according to the mild-moderate-severe severity scale below. Adverse events will be coded using the Medical Dictionary for Regulatory Activities (MedDRA) using the following definitions:

1. **MILD:** Adverse events and/or symptoms recorded in the medical record where no therapy was given to treat the event or where an over-the-counter medication/intervention **ONLY** was given to treat the event.
2. **MODERATE:** Adverse events and/or symptoms recorded in the medical record requiring prescription medication treatment.
3. **SEVERE:** Adverse events and/or symptoms requiring any study drug discontinuation will be defined and coded as severe. ANEMIA events requiring blood transfusion will be coded as severe.

6.1.3 Relationship to Study Drug

Assessment of relatedness will be made with respect to the stage of the trial that the subject is in (screening, waiting list, or post-transplantation) and further with respect to whether the event was related to G/P where applicable. The investigator will use the following definitions to assess the relationship of the adverse event to the use of G/P:

Reasonable Possibility	An adverse event where there is evidence to suggest a causal relationship between the study drug and the adverse event.
No Reasonable Possibility	An adverse event where there is no evidence to suggest a causal relationship between the study drug and the adverse event.

For causality assessments, events assessed as having a reasonable possibility of being related to the study drug will be considered "associated." Events assessed as having no reasonable possibility of being related to study drug will be considered "not associated." In addition, when the investigator has not reported a causality or deemed it not assessable, the sponsor will consider the event associated.

For serious adverse events, if an investigator's opinion of relatedness is "no reasonable possibility of being related to study drug" an "Other" cause of event must be provided by the investigator. After adverse event data is abstracted from the submitted records, the site investigator/ clinician designee will be provided an adverse event listing to assess relationship of the adverse event to study drug.

6.1.4 Adverse Event Reporting

For this study, the AE reporting period will be divided based on the three phases of the study.

Pre-Treatment Phase

Screening phase: When all screening tests have been done, we will assess for any AEs related to the screening tests at the time of communication with the subject about whether he/she is official eligible or ineligible for the study.

Pre-existing Condition: A pre-existing condition is one that is present at the start of the study. A pre-existing condition should be recorded as an AE if the frequency, intensity, or the character of the condition worsens during the study period.

Waitlist phase: We will only capture AEs that are pertinent to the study. Specifically, the following will be captured:

1. Patient death,
2. Patient develops a condition that would exclude that subject from the study,
3. Patient is de-listed (taken off the kidney transplant waitlist)
4. Patient is made inactive on the transplant waitlist
5. Serious Adverse events and non-SAE hospitalizations; these will be categorized as “pre-transplant” (vs. “post-transplant”) and “pre-study drug” (vs. “post-study drug”)

In order to ascertain these events, we will review the patient’s medical history by phone every 2 months and in person every 6 months that they are on the wait list.

Treatment Phase in Arm 1

Immediate Post-transplant phase:

From the date of transplant with a HCV RNA-positive kidney to 1 day before first administration of the study drug, we will collect SAEs and clinical outcomes and data, including death, graft failure, acute allograft rejection, delayed graft function, eGFR, ALT elevation > 5 x ULN, SAEs.

HCV Treatment Phase

The following additional data will be collected from Day 1 of HCV treatment to 30 days following last dose of HCV treatment:

All adverse events will be collected and clinical outcomes, including death, graft failure, acute allograft rejection, delayed graft function, ALT elevation > 5 x ULN, SAEs, sclerosing cholestatic hepatitis and extrahepatic manifestations of HCV, and data of eGFR and proteinuria. An assessment for causality to transplant, HCV infection, or study drug G/P will be made. Grade 3 or greater treatment-emergent laboratory abnormalities from the first dose of G/P through 2 days post dosing will also be collected and summarized. Events of sclerosing cholestatic hepatitis and extrahepatic manifestations of HCV infection will only be collected in ARM 1 subjects and subset of ARM 2A subjects who develop HCV viremia.

Post-Treatment Phase in Arm 1

Post HCV treatment Phase: From 30 days post last dose of HCV treatment to 1 year post kidney transplant (last study visit), the following outcomes and other data will be collected: death, graft failure, acute allograft rejection, delayed graft function, ALT elevation > 5 x ULN, SAEs, sclerosing cholestatic hepatitis and extrahepatic manifestations of HCV. eGFR and proteinuria will be collected at specific visits. All SAEs will be assessed at every clinic visit when the subject is seen by a member of the study team.

All unresolved AEs considered possibly, probably, or definitely related to the study drug or to HCV infection should be followed by the investigator until the events are resolved, the subject is lost to follow-up, or the AE is otherwise explained.

The investigator will notify the IRB of any death or SAE occurring at any time after a subject has discontinued or terminated study participation that may reasonably be related to this study. The IRB will also be notified if the investigator should become aware of the development of cancer or of a congenital anomaly in a subsequently conceived offspring of a subject that has participated in this study.

6.1.5 Serious Adverse Event Reporting

In the event of a serious adverse event, whether associated with study drug or not, the Investigator will notify the Sponsor within 24 hours of the site being made aware of the serious adverse event by submitting the available serious adverse event data to:

Email to: [contact]

For safety concerns, contact the physician listed below:

[name]

Office: [contact]

[contact]

Email: [contact]

If an ongoing SAE changes in its intensity or relationship to study drug or if new information becomes available, a follow-up SAE report should be submitted within 24 hours using the same procedure used for transmitting the initial SAE report. All SAEs should be followed to resolution or stabilization.

The MGH designated Medical Monitor or delegate from the sponsor must also report any serious adverse event in a subjects on G/P treatment (on G/P treatment period includes day 1 of G/P dosing to 30 days after last G/P dose) to AbbVie within 24 hours after receipt of the serious adverse event information from the study site.

6.1.6 Pregnancy

Female subjects should avoid pregnancy starting with screening and through 30 days after completion of study drug.

Pregnancy in a study subject must be reported to the sponsor within 1 working day of the site becoming aware of the pregnancy. Administration of study drug may be continued at the investigator's discretion after discussion with the subject, if the benefit of continuing therapy is felt to outweigh the risk (Section 5.4.1). If a subject is discontinued, the subject will be monitored for SVR in the Post-Treatment Period as described in Section 5.1.3.

Information regarding a pregnancy occurrence in a study subject and the outcome of the pregnancy will be collected for pregnancies occurring up to 30 days after the end of treatment.

Pregnancy in a study subject is not considered an adverse event. However, the medical outcome of an elective or spontaneous abortion, stillbirth or congenital anomaly is considered a serious adverse event and must be reported to the sponsor within 24 hours of the site becoming aware of the event.

In the peri-transplant and post-kidney transplantation period, standard of care is to avoid pregnancy during the first year because of potential negative effects on the allograft and because of the common utilization of teratogenic medications such as mycophenolate mofetil. In the post-transplant period, clinical sites will follow their own standard of care protocols regarding screening for pregnancy and robust contraceptive counselling.

6.1.7 Toxicity Management

For the purpose of medical management, all adverse events and laboratory abnormalities that occur during the study must be evaluated by the investigator. Only lab abnormalities that are deemed clinically significant or require intervention are classified as adverse events. All adverse events and laboratory abnormalities will be managed and followed to a satisfactory clinical resolution. A toxicity is deemed "clinically significant" based on the medical judgment of the investigator.

To facilitate this process in a pragmatic study, after adverse event data is abstracted from the submitted records, the site investigator/clinician designee will be provided an adverse event listing to assess relationship of the adverse event to study drug. The site will also upload signed central lab reports where the investigator completed the evaluation of clinical significance of abnormal results. Actions taken for clinically significant abnormal

laboratory results and/or adverse events will be recorded in the site medical record or source, and entered into the eCRFs.

6.1.8. Management of ALT elevations while on study drug G/P

If a subject experiences a post-baseline increase in ALT to $> 5 \times \text{ULN}$ which is also $> 2 \times$ baseline value, the subject should have a confirmatory ALT measurement performed.

If the ALT increase is confirmed to be $> 5 \times \text{ULN}$ which is also $> 2 \times$ baseline value, the recommendations below should be followed:

- Evaluate for alternate etiology of ALT elevation; document in the source, update the medical history and concomitant medications eCRF (if applicable), and obtain additional testing as appropriate (e.g., hepatitis B panel).
- Manage the subject as medically appropriate.
- Repeat ALT, AST, total and fractionated bilirubin, alkaline phosphatase and INR within 1 week. Repeat liver chemistries as indicated until resolution.
- Discontinue study drugs if any of the following is observed at any time:
 - ALT level is $\geq 20 \times \text{ULN}$ in the absence of an alternate etiology.
 - Increasing direct bilirubin or INR or onset of symptoms/signs of hepatitis.

At the discretion of the investigator alternate management of ALT increases is permitted with approval of the Principal Investigator ([name]) at MGH.

6.1.9. Management of suspected kidney rejection while on study drug G/P

If at any time a site investigator suspects rejection of the transplanted kidney while the subject is receiving study drug, then dose adjustment of immunosuppressants may be performed per the site investigator's usual practice and the event captured on eCRF.

If the abnormality is non-responsive to immunosuppressant adjustment and/or if the site investigator wishes to empirically augment the immunosuppressive regimen, e.g., by

commencement of high dose steroids or to add specific anti-rejection agents but without the availability of a biopsy of the transplanted organ confirming rejection, then change in follow-up procedures and antiviral treatments may be considered by the site investigator, as appropriate.

If the site investigator wishes to pursue alternative management of study drugs in this setting the Principal Investigator should be contacted to obtain approval.

If a biopsy of the transplanted kidney is performed as part of the evaluation of rejection and the histologic findings are consistent with rejection as determined by the local pathologist, the site investigator should follow the usual management of rejection and continuation of study drugs should be per investigator discretion. If the site investigator wishes to pursue alternative management of study drugs in the setting of histologically confirmed rejection, then the Principal Investigator should be contacted to obtain approval. Biopsy tissue from the transplanted organ obtained during the trial to evaluate rejection or other pathologic process should be read locally and the result recorded in the subject source documents. Because of the potential impact of discontinuation (or interruption) of study drugs on immunosuppressant levels, investigators should ensure that a plan for appropriate immunosuppressant dose modification is in place and that this plan is communicated to the subject.

6.2. Product Complaint

6.2.1 Definition

A product complaint is any complaint (see Section 6.0 for the definition) related to the study drug product(s). For a product this may include, but is not limited to, damaged/broken product or packaging, product appearance whose color/markings do not match the labelling, labelling discrepancies/inadequacies in the labelling/instructions (e.g. printing illegible), or missing components/product, or packaging issues. Any product complaints identified centrally in the submitted medical records will be abstracted into the study database.

6.2.2 Reporting

Product complaints concerning the investigational product must be reported to the sponsor within 24 hours of the time it is observed. If the data is abstracted centrally from the submitted medical records, it should be reported via the product complaint form. Product complaints occurring during the study will be followed up to a satisfactory conclusion via specific query to the site for any available clinical information. All follow up information is to be reported to the sponsor and documented in the source medical record. Product complaints associated with adverse events will be reported in the study summary. All other complaints will be monitored on an ongoing basis.

Product complaints may require return of the product with the alleged complaint condition. In instances where a return is requested, every effort should be made by the investigator/site to return the product within 30 days. If returns cannot be accommodated within 30 days, the site will need to provide justification and an estimated date of return.

The description of the complaint is important for AbbVie in order to enable AbbVie to investigate and determine if any corrective actions are required.

7.0 Major Protocol Deviations

The investigator should not implement any major deviation from the protocol without prior review and agreement by the Sponsor and in accordance with the Independent Ethics Committee (IEC)/Independent Review Board (IRB) and local regulations, except when necessary to eliminate an immediate hazard to study subjects. When a deviation from the protocol is deemed necessary for an individual subject, the investigator must contact the following personnel:

[name].

If by e-mail: [contact]

If by [contact]

Such contact must be made as soon as possible to permit a review by the sponsor to determine the impact of the deviation on the subject and/or the study. Any significant protocol deviations affecting subject eligibility and/or safety must be reviewed and/or approved by the IEC/IRB and regulatory authorities, as applicable, prior to implementation.

8.0 Statistical Methods and Determination of Sample Size

In some analyses below, Arm 2 will be further broken down by category:

- A. subjects who receive a kidney from a study-eligible HCV RNA-negative/ HCV Ab-positive donor
- B. subjects who receive a standard of care kidney transplant
- C. subjects who were not transplanted within 1 year of consent

8.1 Statistical and Analytical Plans

The data analysis will be generated using SAS version 9.4 or higher for windows and/or STATA software version 14.0 or higher (StataCorp LP, College Station, TX). SAS Institute Inc. SAS and all other SAS Institute Inc. product or service names are registered trademarks or trademarks of SAS Institute Inc., Cary, NC, USA. All statistical tests (if applicable) and confidence intervals will be two-sided with an alpha level of 0.05.

Descriptive statistics will be provided, such as the number of observations (N), mean, and standard deviation (SD) for continuous variables and counts and percentages for discrete variables.

The efficacy and safety of the “reactive” G/P treatment of patients who become HCV RNA-positive after receiving a kidney from a study eligible HCV RNA-negative/HCV Ab-positive donor in Arm 2A are not an objective of this study, and they are not included in assessments of efficacy or safety described below. The time to transplant and clinical outcomes and data post-transplant from patients in Arm 2A are included in those secondary endpoints.

The primary analysis will occur after all recipients of HCV RNA-positive kidneys in Arm 1 have completed post-treatment week 12 visit (corresponding to SVR₁₂ data collection) or prematurely discontinued study. The primary analysis of SVR₁₂ will be performed on the intention-to-treat (ITT) population defined as all enrolled subjects who received a study eligible HCV RNA-positive kidney and received at least one dose of G/P according to actual treatment received (Arm 1).

No data will be imputed for any efficacy or safety analysis except for analyses of SVR endpoints (HCV RNA data). HCV RNA values will be selected for the analyses of all SVR endpoints (e.g., SVR₄ and SVR₁₂, SVR₂₄) based on defined visit windows. A backward imputation method will be used to impute missing responses for SVR analyses. Additional details of analyses to be performed will be specified in the Statistical Analysis Plan.

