Subjects who are transplanted with kidneys from HCV RNA-positive donors in Arm 1 will be followed for 1 year after the date of transplantation to evaluate safety, graft survival, mortality, allograft rejection, and potential hepatic and extrahepatic manifestations of HCV infection. All recipients of Arm 1 HCV RNA-positive kidneys will be assessed for SVR-12 after G/P treatment. Scheduled visits for subjects who accept an organ from HCV RNA-positive donors in Arm 1 and receive G/P treatment will consist of screening, day of transplant, day 1 of G/P treatment, week 1, week 2, week 4, week 6 and week 8 of treatment (planned end of treatment visit) after starting G/P. Additional scheduled visits will take place at weeks 4, 12 and 24 following completion of the G/P treatment and week 52 (1 year) after transplant. Subjects treated with G/P who experience virological failure will be evaluated for the emergence/persistence of direct-acting antiviral agent (DAA)-resistant viral variants, and suitable retreatment will be offered to study participants.

All subjects in study arm 2 will be followed for a minimum of 1 year from enrollment. In addition, subjects in study arm 2A who received a kidney from an HCV RNA-negative/HCV Ab-positive donor will be followed for a minimum of 24 weeks after the date of transplantation or 1-year post enrollment, whichever is longer, to evaluate safety, graft survival, mortality, and allograft rejection, and potential development of HCV viremia. Study visits for patients receiving a HCV RNA-negative/HCV Ab-positive kidney transplant in Arm 2A will take place at weeks 1, 4, 8, 12, and 24 weeks after transplantation. If a recipient of an HCV RNA-negative/HCV antibody-positive kidney in Arm 2A develops HCV infection within the first 24 weeks of follow-up after transplantation, that recipient will be offered treatment with G/P for 8 weeks. G/P treatment will be administered and subject will be followed as per local transplant center

standard-of-care and study-objective pertinent data from the G/P treatment period and post treatment period will be collected. This includes SAEs, treatment-emergent Grade 3 or greater laboratory abnormalities, and HCV RNA 12 weeks post G/P treatment completion.

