The primary efficacy endpoint is sustained virologic response 12 weeks post dosing (SVR₁₂), defined as HCV RNA < LLOQ 12 weeks after the last actual dose of G/P. The SVR₁₂ rate will be determined from all enrolled subjects who received an HCV RNA-positive kidney in Arm 1 and received at least one dose of G/P study drug along with a two-sided 95% confidence interval. The confidence interval for the SVR₁₂ rate will be calculated using Wilson's score method.

The secondary efficacy endpoints for recipients of kidney transplants from HCV RNA-positive donors in Arm 1 are:

1. The percentage of subjects with on-treatment virologic failure;
2. The percentage of subjects with post-treatment virologic relapse.

Additional efficacy analyses will be performed.

Clinical endpoints:

Secondary endpoints for the secondary objectives are:

1. Among all subjects enrolled in the study who receive a kidney transplant, the time to kidney transplant and cumulative incidence of each type of transplant will be determined for: study-eligible HCV RNA-positive kidneys (Arm 1), study-eligible HCV RNA-negative/HCV Ab-positive kidneys (Arm 2A), and standard of care kidney transplants (Arm 2B).
2. The number and percentage of subjects with clinical outcomes while on the

waitlist (SAEs, delisting from waitlist, death) among subjects who receive an HCV RNA-positive kidney in Arm 1 and among those subjects who do not receive a study eligible HCV RNA-positive kidney (all Arm 2 subjects) overall and with breakdown by the category in Arm 2 (2A, 2B and 2C). In addition, the total number of inpatient hospital days while on waitlist in those who did receive a study eligible HCV RNA-positive kidney (Arm 1) and total inpatient hospital days in those who did not (Arm 2) overall and with breakdown by categories of Arm 2 will be summarized descriptively.

3. The number and percentage of subjects with the following clinical outcomes and data post-transplant as applicable: death, graft failure, acute allograft rejection, delayed graft function, ALT elevations > 5x ULN, and SAEs. The difference in the overall percentage of subjects with clinical outcomes and data post-transplant between Arm 1 and Arms (2A + 2B1 – 2B4) will be assessed by logistic regression with Arm as a factor and appropriate covariates to adjust for possible differences between Arms including waiting list priority, blood group, geographic region and sensitization as appropriate.

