Eligible subjects will initiate G/P 300 mg/120 mg QD for 8 weeks early after kidney transplantation. Day 3 post-transplant is targeted for the start of G/P treatment for HCV RNA-positive kidney recipients, with the conditions met that the subject should be out of the ICU, able to eat and drink and take medications orally, and in the judgement of the investigator, starting oral G/P treatment is safe for the subject.

A delay in commencing G/P after day 3 should only take place because the responsible site investigator and/or responsible clinicians believe that G/P cannot be safely administered or because of a high probability that G/P will subsequently need to be discontinued or held for prolonged period because the patient is likely to experience clinical deterioration. In the case of any patient who has not started G/P by day 3 after transplantation, the site investigator will discuss that case with the Principal Investigator [name], or delegate, and develop and document a plan to start G/P at a later time.

Post Treatment (PT) Period for recipients of HCV RNA-positive kidneys in Arm 1:

Subjects who complete or prematurely discontinue G/P treatment will be followed for 24 weeks after their last dose of study drug to evaluate efficacy and to monitor HCV RNA and the emergence and persistence of viral substitutions in the NS3 and NS5A, and subjects will be followed up at 1 year post the date of kidney transplant to assess graft function and survival and anti-HCV antibody serology.

Figure 1A: Overall Study Schematic

[figure not shown]
Treatment and PT Period for Study Arm 2A recipients of HCV RNA-negative/HCV antibody-positive kidneys:

Eligible subjects will be followed for 24 weeks after transplantation or 12 months after enrollment, whichever is longer, with surveillance for HCV infection using HCV RNA testing on week 1, week 4 (usual care), and week 24 (Figure 1B) after transplantation. A maximum number of up to n=20 subjects who are enrolled into the study can accept a study-eligible kidney from an HCV RNA-negative/HCV antibody-positive donor and be assigned to Arm 2A and will be followed in the study for 24 weeks post-transplant. The last study-eligible kidney transplant from an HCV RNA-negative/HCV antibody-positive donor in Arm 2A must occur no later than 24 weeks after the date of the 30th kidney transplant from an HCV RNA-positive donor in Arm 1 (see also section 5.1.5).

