8.1.2 Efficacy

All efficacy analyses will be performed on the ITT population, unless otherwise specified. Plasma HCV RNA levels will be determined for each sample and measured using standard of care in the clinical site labs. HCV RNA \geq the lower limit of quantification (LLOQ) are all quantifiable values.

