Clinical outcomes post-transplant will include death, graft failure, acute allograft rejection, delayed graft function, ALT elevation > 5 times the upper limit of normal, and SAEs. In addition, HCV-infection related events of fibrosing cholestatic hepatitis and extrahepatic manifestations of HCV infection collected for Arm 1 subjects and only for Arm 2A subjects who develop HCV viremia will also count as clinical outcomes. The number and percentage of subjects with each and any clinical outcomes will be summarized for those who receive an HCV RNA-positive kidney (Arm 1) versus Arm 2 subjects combined and broken down (2A and 2B) as applicable. The difference in the overall percentage of subjects with clinical outcomes post-transplant in Arm 1 vs Arm 2A + 2B will be assessed by logistic regression with Arm as a factor and including appropriate covariates to adjust for possible differences between Arms including waiting list priority, blood group,

geographic region and sensitization, as appropriate given sample size and other statistical considerations. In addition, to include any clinical outcomes due to being treated with G/P, another summary of clinical outcomes post-transplant will include any study drug (G/P) related severe treatment emergent adverse events for Arm 1 subjects, and another will include events of treatment emergent Grade ≥ 3 laboratory values and related severe treatment emergent adverse events as clinical outcomes for Arm 1 subjects.

Analyses of the eGFR outcome will be calculated eGFR using the 4-variable MDRD equation. Mean (SD) eGFR will be summarized at appropriate visits and compared between Arms. Specifically, mean eGFR at 24 weeks/6-months post-transplant and 1 year post transplant will be compared between Arm 1 transplant recipients and the combined group of Arm 2A and 2B transplant recipients (2B1-2B4). As a secondary approach, mean eGFR at 24 weeks/6-months post-transplant will be compared between Arm 1 recipients and Arm 2A and 2B kidney recipients limited to those 2A and 2B recipients who did not develop HCV infection.

We will also compare estimated proteinuria between Arms 1 and 2A, including a count of individuals with >1000 mg/day estimated proteinuria. Proteinuria will be estimated using spot protein:Cr ratio.

An exploratory analysis will summarize the number and percentage of subjects with clinical outcomes post kidney transplant for the subgroups of Arm 2B.

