8.3 Assignment of Participants to Study Arms: Methods

This is a two-arm study. All eligible subjects who entered the study will be observed. Observed subjects who accept a study-eligible HCV RNA-positive kidney allograft offer will be assigned to the G/P treatment Arm 1 and followed in that Arm up until 1 year post-transplant. All other enrolled study subjects will remain in Arm 2 of the study (see Figure 1A).

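### The set labelled ITT requires at least one G/P dose, so undosed recipients drop out of every SVR12 analysis and out of the SAP's death and graft-failure analyses, in conflict with Protocol 8.1.4

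*Protocol*

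**What the plan says.** - **Primary set.** Protocol 8.1 defines the ITT population as "all enrolled subjects who received a study eligible HCV RNA-positive kidney and received at least one dose of G/P". The synopsis repeats the condition for the SVR12 rate: subjects must have "received at least one dose of G/P study drug along with a two-sided 95% confidence interval". Protocol 8.1.2 then states: "All efficacy analyses will be performed on the ITT population, unless otherwise specified".
- **Arm 1.** Protocol 8.3 fixes membership earlier: "Observed subjects who accept a study-eligible HCV RNA-positive kidney allograft offer will be assigned to the G/P treatment Arm 1". Protocol 8.1 nevertheless attaches the Arm 1 label to the dosed set, those who "received at least one dose of G/P according to actual treatment received (Arm 1".
- **Death and graft failure in the SAP.** Parts 10 and 11 analyse them as time to event by Cox regression in Arm 1 – ITT. The SAP does not define ITT and gives no time origin for these two rows. Parts 12 to 14 (delayed graft function, rejection, ALT) use plain Arm 1, and Part 15 (SAEs) uses all patients by arm.
- **Death and graft failure in the Protocol.** Section 8.1.4 has post-transplant outcomes "summarized for those who receive an HCV RNA-positive kidney (Arm 1) versus Arm 2 subjects combined", with no dose condition. Section 5.3.4 collects them in all transplanted subjects. Section 6.1.4 collects them in Arm 1 from the transplant date to the day before first dose.
- **Sensitivity analysis.** The only one for SVR12 (Protocol 8.1.2.3) removes further subjects from the ITT set: those without SVR12 for reasons other than virologic failure or relapse.

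**The concern.** Dosing is targeted for day 3 and depends on the recipient's state after surgery: out of the ICU, eating and drinking, taking oral medication, and judged safe to start. Protocol 5.1 also allows a later start where G/P would probably have to be stopped or held "because the patient is likely to experience clinical deterioration". Entry to the analysis set is therefore an event after transplant that is related to prognosis.

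For death this has a definite effect. A recipient who dies before the first dose cannot be in the set. If the clock in Part 10 starts at transplant, the interval to first dose is death-free by construction (immortal time). If it starts at first dose, the early risk period is not analysed. In both cases the death is missing from that analysis.

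For SVR12, a recipient who was given a viremic kidney and never treated would appear in no planned denominator. With 30 recipients, one such patient decides whether the headline rate can read 100%.

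**Working it through.** **Inputs.** Planned Arm 1 size is 30 (Protocol 5.1.5). Intervals are two-sided at 0.05 (Protocol 8.1). The SVR12 interval is Wilson in Protocol 8.1.2.1 and exact binomial in SAP Part 1, so both are shown. The number never dosed is not given; I assume 0 to 3 of 30 and that every dosed subject is cured.

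**The plan's own figure.** Table 10 gives one-sided 95% Wilson lower bounds at n = 30 of 93.8, 85.4, 81.0, 76.9 and 73.0% for 30 down to 26 cures. One-sided Wilson (z = 1.645) gives 91.7, 86.4, 81.7, 77.4 and 73.4%, so the table does not reproduce. That is a separate matter and nothing below depends on it.

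**Wilson lower limit**, with p = x/n and z = 1.96 (z² = 3.8416):

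L = [p + z²/(2n) − z·√(p(1−p)/n + z²/(4n²))] / (1 + z²/n)

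When x = n this reduces to n/(n + z²).

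- 30/30: 30/33.8416 = 88.6%
- 29/29: 29/32.8416 = 88.3%
- 28/28: 28/31.8416 = 87.9%
- 29/30: centre (0.9667 + 0.0640)/1.1281 = 0.9137; half-width 1.96 × √(0.001074 + 0.001067)/1.1281 = 0.0804; L = 83.3%
- 28/30: centre (0.9333 + 0.0640)/1.1281 = 0.8841; half-width 1.96 × √(0.002074 + 0.001067)/1.1281 = 0.0974; L = 78.7%

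| Undosed of 30 (assumed) | Dosed set as planned | Wilson / exact lower limit | All recipients, undosed = non-response | Wilson / exact lower limit |
|---|---|---|---|---|
| 0 | 30/30 = 100% | 88.6 / 88.4% | 30/30 = 100% | 88.6 / 88.4% |
| 1 | 29/29 = 100% | 88.3 / 88.1% | 29/30 = 96.7% | 83.3 / 82.8% |
| 2 | 28/28 = 100% | 87.9 / 87.7% | 28/30 = 93.3% | 78.7 / 77.9% |
| 3 | 27/27 = 100% | 87.5 / 87.2% | 27/30 = 90.0% | 74.4 / 73.5% |

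Each undosed recipient takes 3.3 points off the all-recipient rate and about 4 to 5 points off its Wilson lower limit. The dosed-set rate does not move, and its lower limit falls by 0.3 to 0.4 points.

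**One death before dosing.** As planned: 0/29, exact upper limit 1 − 0.025^(1/29) = 11.9%. In all recipients: 1/30 = 3.3%, exact upper limit 17.2%.

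**How likely is at least one undosed recipient?** The chance is 1 − (1 − q)^30, where q is the assumed chance of never starting: q = 1% gives 26%, 3% gives 60%, 5% gives 79%.

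**Which outcomes are affected.** Death before first dose: always outside the ITT set. Graft loss before first dose: outside only if the recipient is then never dosed, because membership needs a dose and not a working graft. Any event after one dose: inside. Late start: inside.

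**The case against.** The primary objective (Protocol 4.1) concerns an 8-week treatment with G/P, and SVR12 is timed from the last actual dose, which an undosed person does not have. A dosed set is a legitimate answer to that question, and the condition is openly stated in two places. The synopsis sentence "All recipients of Arm 1 HCV RNA-positive kidneys will be assessed for SVR-12 after G/P treatment" does not contradict it, since it presupposes treatment. This stands, and it is why the dosed set should remain primary.

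Three stronger readings are tempting, and the documents do not support them.

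- A reader might infer that early deaths and graft losses vanish from the safety results altogether. They do not. Protocol 8.1.4 counts them in all recipients, sections 5.3.4 and 6.1.4 collect them, and SAP Parts 12 to 15 carry no ITT restriction. Death is itself an SAE under Protocol 6.1.1.2.
- A reader might infer that every graft loss before dosing is excluded by definition. The starting conditions in Protocol 5.1 do not require graft function, and the Introduction describes G/P as suitable for patients on dialysis.
- A reader might take the deterioration clause as a forecast of undosed recipients. It governs delay, requires a documented plan to start later, and timing of initiation is a planned SVR12 subgroup (Protocol 8.1.2.4).

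It is also fair to say that the SAP is a draft summary table, so applying the Protocol 8.1 definition to Parts 10 and 11 is an inference. It is the only ITT definition in either document, though, and the SAP's use of plain Arm 1 in Parts 12 to 14 suggests that the two labels are meant to differ.

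**Conclusion.** The point holds in a limited form. The ITT set is a treated set. It excludes from SVR12 and from SAP Parts 10 and 11 any recipient who dies before the first dose and any recipient never dosed for another reason, including one who loses the graft and is never dosed. On death and graft failure the SAP conflicts with Protocol 8.1.4, and on Arm 1 membership Protocol 8.1 conflicts with 8.3. No SVR12 analysis includes undosed recipients, and the one sensitivity analysis moves further from them.

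The size is conditional. It is nil if all recipients are dosed. With one or two undosed and all others cured, the Wilson lower limit is 5.0 points (88.3 − 83.3) or 9.2 points (87.9 − 78.7) higher on the dosed set than in all recipients. The never-dosed counts are my assumption. The exclusion rule itself is in the text and needs no assumption beyond reading the SAP's ITT as the Protocol's.

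**What to change.** 1. Run SAP Parts 10 and 11 on all Arm 1 recipients, with time zero stated as the date of transplant. This brings them into line with Protocol 8.1.4 and 8.3 and uses data that section 6.1.4 already collects.
2. Keep the dosed set for the primary SVR12 analysis, but call it modified ITT in both documents, and stop using Arm 1 as a synonym for it in Protocol 8.1.
3. Add one supportive SVR12 analysis in all Arm 1 recipients, counting undosed recipients as non-responders and listing the reason each was not dosed.

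The cost is SAP wording and one extra table. The supportive SVR12 rate may be lower than the primary rate. No new data collection is needed, and if everyone is dosed the results do not change. Fixing the denominators in advance also removes the option of choosing between them once the data are known.
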